Study design	
As per the USM follow-up notification dated 06-Dec-2022, the study treatment has been permanently discontinued and only Cohort 1 was enrolled. Participants who received active treatment (branaplam) will remain in the study for follow-up for approximately one year following initial treatment discontinuation. OLE is no longer applicable.
 
Pre-USM:
 
This study is a randomized, double-blind, placebo-controlled study with a variable treatment duration (between approximately 17 weeks to approximately 53 weeks) for the core period and a one-year OLE in approximately 75 early-stage manifest HD patients.
 
After Screening period and BL assessments, this study will be conducted in two Treatment Periods:
 
• The Core Period consists of a 17-week double-blind, placebo-controlled, Dose Range Finding (DRF) portion of the study, followed by a Blinded Extension (BE) of variable duration (up to approximately 53 weeks; duration is dependent on timing of randomization and recruitment rate). The DRF Period will evaluate the safety, tolerability, pharmacokinetic(s) (PK) and pharmacodynamic(s) (PD) of branaplam, as well as determine the optimal dose(s) to explore in further clinical evaluations using all available data collected at the time the last randomized patient in the study completes the Week 17 visit assessments which captures a full 16 weeks of treatment with study drug.• The OLE is a one-year open-label extension to assess both long term safety and tolerability, as well as the efficacy of the recommended optimal dose(s) for branaplam. If branaplam development in HD remains ongoing at the end of the OLE, the study will either be (a) amended to extend the OLE beyond a year, or (b) a separate extension study will be initiated to offer continued access to branaplam. Study participants from the OLE may be eligible to roll over into this separate extension study. 
The study design uses a staggered cohort approach, allowing safety and tolerability of lower doses to be assessed before randomizing subjects to higher doses.
 
The Core Period consists of 3 treatment arms; each treatment arm will enroll approximately 25 patients, dependent on the total number of cohorts initiated.
 
Treatment arms are defined as:
 
• Cohort 1: Treatment Arm A: Branaplam 56 mg oral solution or matching placebo (PBO), once weekly• Cohort 2: Treatment Arm B: Branaplam 112 mg oral solution or matching PBO, once weekly• Cohort 3:
• Treatment Arm C: Branaplam 154 mg oral solution or matching PBO, once weekly or• Treatment Arm X: Branaplam 84 mg oral solution or matching PBO, once weekly or• Treatment Arm Y: Branaplam 28 mg oral solution or matching PBO, once weekly 
At the time of the Cohort Gating Assessments (CGAs), all available data will be reviewed from a safety and dose finding perspective by an independent Sponsor team to support the decision to open the next cohort. The independent Data Monitoring Committee (DMC) will review the data separately. The decision to open a new cohort will be made by the Sponsor in consultation with the DMC.
 
Cohort 1 includes Treatment Arm A (56 mg or matching placebo). Based on the results from the review of the data during CGA 1, a decision will be made regarding the initiation of Cohort 2 (Treatment Arm B, 112 mg or matching placebo). Based on the results from the review of the data during CGA 2, a decision will be made to select the Treatment Arm in Cohort 3. If Cohort 3 is initiated, and based on the data review during CGA 2, the decision will be made to initiate the next higher dose

---------------------	---

	
(Treatment Arm C, 154 mg or matching placebo) or an intermediary dose (Treatment Arm X, 84 mg or matching placebo) or a lower dose (Treatment Arm Y, 28 mg or matching placebo).
 
Participants will be randomized in an equal randomization rate among the open treatment arms, and then in a 4:1 ratio for active vs. placebo within each arm.
 
After a participant completes the DRF period (Week 17) he/she will seamlessly transition to the BE, by continuing on his/her blinded DRF treatment. All patients will remain in the BE until the results of the IA are available and the recommended optimal extension dose(s) is/are selected for OLE. Duration in the BE is therefore variable, longer for those that were randomized earlier in the study.
 
After the last randomized participant in the study completes all the DRF (Week 17) assessments, an un-blinded IA will be conducted. All data available at this time, including, but not limited to safety/tolerability as well as mHTT and total HTT lowering in CSF, plasma [REDACTED] will be assessed to determine optimal dose(s) for OLE. After the IA and confirmation of selected dose(s), all patients from the blinded Core Period will roll over to OLE; patients will be reassigned from their blinded Core Period dosing onto the newly selected open label OLE dose(s).
 
OLE is a one-year open label treatment and safety monitoring part of the study.

Population	
Approximately 75 male or female patients with confirmed Stage 1 or 2 HD and a UHDRS total functional capacity (TFC) score of >8 will be enrolled in this study to allow for approximately 25 participants per treatment arm. Fewer participants will be enrolled if all treatment arms are not opened.
 
Manifest patients with a TFC >8 are selected because they are late enough in the disease process so that mHTT can be measured in their CSF and clinical symptoms can be readily assessed, and early enough in the disease process so that they can comply with the protocol defined schedule of assessments during Core blinded treatment period (DRF and BE) and be monitored for disease progression and safety throughout the OLE. Eligible patients starting at the age of 25 will be enrolled to avoid the very high CAG repeats associated with early disease onset as these patients could be considered to have a more rapidly progressing phenotype. An age cap of 75 years is employed to avoid age-related comorbidities that typically occur above this age.

Key Inclusion criteria	
As per the USM follow-up notification dated 06-Dec-2022, no further participants will be enrolled in this study.
 
Participants eligible for inclusion in this study must meet all of the following criteria:
 
 1. Signed informed consent must be obtained prior to participation in the study. 2. Must be capable of providing informed consent (in the opinion of the Investigator). 3. Clinically diagnosed Stage 1 or 2 Huntington's disease with a diagnostic confidence level (DCL) = 4 and a Unified Huntington's Disease Rating Scale (UHDRS) Total Functional Capacity (TFC) >8 at screening. 4. Genetically confirmed Huntington's disease, with presence of ≥ 40 cytosine-adenine-guanine (CAG) repeats in the huntingtin gene. 
For participants without prior documentation, a sample must be sent to the central study laboratory and confirmation of the CAG repeat length for these participants must be obtained prior to randomization.
 
For participants with previously existing documentation of their CAG repeat length, it is acceptable to use this prior data to qualify for randomization. These participants must also submit a sample for CAG repeat testing to be conducted by the central study laboratory.
 
 5. Male and female participants between 25 to 75 years of age, inclusive, on the day of Informed Consent signature.
Key Exclusion criteria	
As per the USM follow-up notification 06-Dec-2022, no further participants will be enrolled in this study.
 
Participants meeting any of the following criteria are not eligible for inclusion in this study:

	
1. Use of other investigational drugs within 5 half-lives of the first dose of study drug, or within 30 days, whichever is longer.2. Prior participation in clinical trial investigating a huntingtin-lowering therapy (unless participant received only placebo).3. History of hypersensitivity to any of the study drugs or its excipients or to drugs of similar chemical classes.4a. Participants taking medications prohibited by the protocol. In addition, participants should be on a stable dose and regimen of permitted chronic concomitant medications for at least 6 weeks prior to receiving the first dose of study drug which in the medical judgement of the Investigator is not anticipated to change during the study. If new medications are initiated during Screening, laboratory evaluations must meet eligibility criteria before first dose of study drug.5. Any medical history, lumbar surgery or condition that would interfere with the ability to complete the protocol specified assessments, (e.g., history of brain or spinal injury that would interfere with the lumbar puncture (LP) or CSF circulation, implanted cerebrospinal shunt, conditions precluding MRI scans, herniated disc, etc.).6. History of malignancy of any organ system (other than localized basal cell carcinoma of the skin or in situ cervical cancer), treated or untreated, regardless of whether there is evidence of local recurrence or metastases.7. Participant has other severe, acute or chronic medical conditions including unstable psychiatric conditions, or laboratory abnormalities that in the opinion of the Investigator may increase the risk associated with study participation, or that may interfere with the interpretation of the study results.8. Score "yes" on item 4 or item 5 of the Suicidal Ideation section of the Columbia Suicide Severity Rating Scale (C-SSRS), if this ideation occurred in the past 6 months from the Screening visit, or "yes" on any item of the Suicidal Behavior section, except for the "Non-Suicidal Self-Injurious Behavior" (item also included in the Suicidal Behavior section), if this behavior occurred in the past 2 years.9. Pregnant or nursing (lactating) women. Women of child-bearing potential (WOCB) should not become pregnant during the study or 7 months after stopping study medication.10a. Sexually active males unwilling to use a condom during intercourse while taking study treatment and for 120 days (4 months) after the last dose of the study treatment. A condom is required for all sexually active male participants even if they are surgically sterile with a vasectomy to prevent them from fathering a child AND to prevent delivery of study treatment via seminal fluid to their female partner. In addition, male participants must not donate sperm for the time period specified above. A condom is required to be used also by vasectomized men as well during intercourse with a male partner of the study participant. The branaplam exposure in body fluids is not known. Since branaplam is genotoxic, sexual partners are advised to avoid direct contact with semen of participants, to prevent exposure to the study drug.11a. Women of child-bearing potential, defined as all heterosexually active women physiologically capable of becoming pregnant, unless they are using one highly effective method of contraception during dosing and for 7 months after stopping the study medication. Highly effective methods of birth control are those methods that have a less than 1% chance of an unwanted pregnancy for 1 year. In addition to one highly effective method of contraception, a condom is required for all male partners of female participants to prevent fathering a child AND to prevent exposure of study treatment via vaginal fluid to the partner, until at least 7 months following the last dose of study treatment. WOCB potential must not donate their eggs for 7 months after the last dose of study treatment.
--	---

	
Oral contraception cannot be considered due to potential decreased efficacy as potential drug-drug interactions (DDI) with branaplam.
 
Highly effective contraception methods include:
 
• Total abstinence (when this is consistent with the preferred and usual lifestyle of the participant). [Periodic abstinence (e.g., calendar, ovulation, symptothermal, post-ovulation methods) and withdrawal are NOT acceptable methods of contraception for heterosexually active participants.]• Female sterilization (have had surgical bilateral oophorectomy with or without hysterectomy) total hysterectomy or bilateral tubal ligation at least six weeks before taking investigational drug. In case of oophorectomy alone, only when the reproductive status of the woman has been confirmed by follow up hormone level assessment.• Male sterilization of partners (at least 6 months prior to screening). For female subjects on the study, the vasectomized male partner should be the sole partner.• Use of an intrauterine device (IUD) or intrauterine system (IUS) which is MRI compatible. 
In case local regulations are more stringent than the contraception methods listed above, local regulations apply and will be described in the ICF. Women are considered post-menopausal if they have had 12 months of natural (spontaneous) amenorrhea with an appropriate clinical profile (e.g., age appropriate, history of vasomotor symptoms). Women are considered not of child-bearing potential if they are post-menopausal or have had surgical bilateral oophorectomy (with or without hysterectomy), total hysterectomy or bilateral tubal ligation at least six weeks prior to Screening. In the case of oophorectomy alone, only when the reproductive status of the woman has been confirmed by follow up hormone level assessment is she considered not of child-bearing potential.
 
The branaplam exposure in body fluids is not known. Since branaplam is genotoxic, sexual partners are advised to avoid direct contact with vaginal fluid of participants, to prevent exposure to the study drug.
 
12a. History of:
 
• Gene therapy or cell transplantation or any other experimental brain surgery• Hepatitis B or hepatitis C or serologic evidence for active viral hepatitis (HBsAg and HCVab test)• Immunodeficiency diseases, including a positive human immunodeficiency virus (HIV) test result• Current evidence of drug or alcohol abuse in the 12 months prior to screening, as defined by the Diagnostic and Statistical Manual of Mental Disorders Fifth Text revision (DSM-V) criteria for substance abuse. For former abusers, abstinence should be confirmed by laboratory tests (drug testing and/or carbohydrate deficient transferrin (CDT) level in blood).• Use of Tetra-Hydro-Cannabinoid (THC)/ cannabinoid containing substances is allowed as per local regulations and/or local medical practice if in the opinion of the Investigator, use does not represent an exclusionary condition, does not constitute abuse and does not affect cognition, and provided that participants are currently treated with a stable regimen for at least 12 weeks prior to first dose of study drug. Note: If initiated during the study, use must be withheld for 72 hours prior to any cognitive and/or motor assessments. 
13a. Any surgical or medical condition which might put the participant at risk in case of participation in the study. The Investigator should make this determination in consideration of the participant's medical history and/or clinical or laboratory evidence of any of the following at the Screening visit:
 
• Unstable chronic gastrointestinal condition such as history of Crohn's disease, Ulcerative colitis, poorly controlled Irritable Bowel Syndrome (IBS) or similar chronic gastrointestinal (GI) conditions• Neurologic or neuromuscular conditions other than HD
--	---

	
• History of or physical examination consistent with peripheral neuropathy or nerve conduction findings compatible with electrodiagnostic evidence of neuropathy• Participants who have a known diagnosis of diabetes mellitus or who do not have a known diagnosis of diabetes with a glycated hemoglobin (HbA1c) >6.5%• Lipase, total bilirubin or amylase must not exceed the 1.5x ULN• Liver disease or liver injury as indicated by abnormal liver function tests• Any of the following single parameters in serum of alanine aminotransferase (ALT), aspartate aminotransferase (AST), gamma-glutamyl transferase (GGT), and alkaline phosphatase must not exceed 2.0 x ULN.• History of renal injury / renal disease or presence of severe impaired renal function as indicated by an estimated glomerular filtration rate (eGFR) using the modification of diet in renal disease (MDRD) equation <30 (mL/min/1.73 m²) (allowing for age-related GFR decline in the mild to moderate range) or the presence >3+ proteinuria/ hematuria on a single (one time) repeated urinalysis• Evidence of urinary obstruction potentially leading to an impaired renal function at screening• Diagnosis of testicular atrophy• Diagnosis of primary ovarian failure• Clinically significant retinal abnormalities on ophthalmologic examination by a local Ophthalmologist• Active infection requiring systemic antiviral or antimicrobial therapy that will not be completed at least 3 days prior to first study drug administration (Day 1)• Any objects and/or implants in the body which may be contraindicated for MRI, such as pacemakers and some IUD• Diagnosis of chronic thrombocytopenia or a bleeding disorder 
14a. Cardiovascular exclusion criteria:
 
• History or current diagnosis of electrocardiogram (ECG) abnormalities indicating significant risk or safety concern for study participants such as: History of myocardial infarction, angina pectoris, heart failure, or coronary artery bypass graft (CABG). Screening echocardiogram (ECHO) abnormalities per investigator's medical judgement including but not limited to left ventricular ejection fraction (LVEF) <50%.• Screening or baseline not within normal range Troponin or N-terminal (NT)-pro hormone pro B-type natriuretic peptide (NTproBNP) values• History or concomitant clinically significant cardiac arrhythmias (e.g., sustained ventricular tachycardia, atrial fibrillation, etc.), complete left bundle branch block, high-grade atrioventricular (AV) block (e.g., bifascicular block, Mobitz type II and third-degree AV block).• History of familial long QT syndrome or known family history of Torsade de Pointes, risks for Torsades de Pointes (TdP) including uncorrected hypokalemia or hypomagnesemia, history of clinically significant/symptomatic bradycardia and a family history of idiopathic sudden death.• Resting QT interval corrected by Fridericia's formula (QTcF) ≥450 msec (male) or ≥460 msec (female) at pretreatment [screening or baseline] (as mean of triplicate ECGs), or inability to determine the QTcF interval.• Use of agents known to prolong the QT interval or with a known or possible risk of Torsade de Pointes unless it can be permanently discontinued or replaced with a permitted medication for the duration of study. (See Table 6-2)• Uncontrolled hypertension (average 3 systolic blood pressure [SBP] readings) at screening >140 mmHg or average diastolic blood pressure [DBP] > 90 mmHg excluding values related to white coat syndrome (anxiety-related), per Investigator's judgement.
--	--

	
15a. Any clinically significant hematological abnormality as assessed by the Site Investigator at screening and/or laboratory evidence of any of the following:
 
 • International Normalized Ratio (INR), PT, or APTT that are not within normal ranges • Hemoglobin <110 grams per liter (g/L) (females) or <120 g/L (males) • Platelets $\leq 100 \times 10^9$ Liter (L) • Platelet count $> 500 \times 10^9$/L • Neutrophil count $< 1.5 \times 10^9$/L • Leukocytes $< 3.0 \times 10^9$/L
Study treatment	
As per the USM follow-up notification dated 06-Dec-2022, the study treatment has been permanently discontinued; the last dose administered was 08-Aug-22; and no further enrollment is allowed.
 
The investigational treatment for this study is branaplam and matching placebo. Novartis will supply branaplam and matching placebo in 6 mL vials containing 5 mL of study treatment. The vials will be packed in boxes containing 4 vials each. All eligible participants will be randomized via Interactive Response Technology (IRT) to one of the available treatment arms.
 
At the Week 1 visit, participants will be randomized to one of the following treatment arms in a ratio of 4:1, active vs. PBO:
 
 • Treatment Arm A: 56 mg oral solution or matching PBO, weekly • Treatment Arm B: 112 mg oral solution or matching PBO, weekly • Treatment Arm C: 154 mg oral solution or matching PBO, weekly • Treatment Arm X: 84 mg oral solution or matching PBO, weekly • Treatment Arm Y: 28 mg oral solution or matching PBO, weekly 
Treatment Arm assignment for an individual participant will be determined by which treatment arms are open at the time of the participant screening. For Treatment Arms C, X and Y, only one of the three will be initiated. PBO is embedded within each Treatment Arm.

Efficacy assessments	
Efficacy assessments include the following:
 
 • Unified Huntington's Disease Rating Scales (UHDRS) components: • Total Functional Capacity (TFC) • Total Motor Scale (TMS) • Independence Scale (IS) 
[REDACTED]
 
[REDACTED]
 
[REDACTED]
 
[REDACTED]

Pharmacodynamic assessments	
 • Volumetric MRI • Mutant Huntingtin Protein (mHTT) and total Huntingtin protein (HTT) in CSF, plasma
Pharmacokinetic assessments	
PK samples from plasma and CSF will be obtained from all participants at all dose levels. Branaplam and its metabolite UFB112 will be determined in plasma and CSF by a validated LC-MS/MS method

Key safety assessments	
Safety assessments include the following:
 
Pre-USM:
 
 • Physical Examination • Vital signs • Height and weight • Electrocardiograms (ECGs)

	
25% missed doses (i.e., 4 doses for weekly dosing during DRF period) AND less than 2 consecutive weeks off treatment prior to the Week 17 visit LP.
 
The summary measure: reduction (%) of mHTT protein in CSF from BL to Week 17 visit for various doses (dose-response relationship). The justification is, that the primary estimand targets the treatment effect of branaplam for those who can tolerate it for 16 weeks (with limited interruption/discontinuation) in order to inform the selection of an optimal dose.
 
The primary estimand will only focus on the efficacy of branaplam on the reduction of mHTT in CSF (one of the primary objectives). The safety perspective will be evaluated in parallel. Dose selection for Open Label Extension and subsequent Phase 3 studies will be based on a combination of efficacy and safety results. However, estimands are not defined for the safety objective, safety analyses will be specified. No inferential and model based statistical analyses are planned for any safety or tolerability endpoints.
 
Post USM: Refer to Section 12 Data Analysis and Statistical Methods

Data Monitoring/Other Committee	Yes
Key words	Huntington's disease, branaplam, dose range finding, early manifest, LMI070, safety and tolerability

1 Introduction

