10.2.3 Prospective suicidality assessment

The Columbia-Suicide Severity Rating Scale (C-SSRS) is a questionnaire that prospectively assesses suicidal ideation and suicidal behavior. The C-SSRS must be administered at each visit, including unplanned visits.

The C-SSRS, which uses a semi-structured interview to probe participant responses, will be administered by an individual who has received training and certification in its administration. At the first study visit, the “baseline/screening” version of the C-SSRS will be administered. This version assesses suicidal ideation and suicidal behavior during the participant's lifetime and during a predefined period. At subsequent visits, the “since last visit” version will be administered

If, at any time after screening and/or baseline, the score is “yes” on item 4 or item 5 of the suicidal ideation section of the C-SSRS or “yes” on any item of the suicidal behavior section, the participant must be referred to a mental health care professional for further assessment and/or treatment. The decision on whether the study treatment should be discontinued is to be taken by the Investigator in consultation with the mental health professional to whom the participant is referred.

In addition, all life-threatening events must be reported as SAEs. For example, if a participant answers “yes” to one of the questions in the suicidal behavior section, an SAE must be reported if the event was life-threatening. All events of “Non-Suicidal Self-Injurious Behavior”

(question also included in the suicidal behavior section) should be reported as AEs and assigned the appropriate severity grade.

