### **Summary tables**

- Absolute values and change from baseline will be summarized for continuous laboratory parameters by visit.
- For selected laboratory tests, the number and percentage of participants with newly occurring or worsening laboratory/liver enzyme abnormalities meeting the clinically notable criteria at any time post baseline will be summarized. Clinically notable criteria are defined in [Appendix 5.5](#).

For a participant to meet the criterion of a newly occurring clinically notable value, the participant needs to have a baseline value that is not clinically notable for that parameter. For a participant to meet the criterion of a worsening clinically notable value, the participant needs to have a baseline value that is clinically notable and also have a worse post-baseline value. For participants with missing baseline value, any post-baseline notable value will be considered as newly occurring.

For each participant, all applicable post-baseline values (including unscheduled or unplanned visits) will be checked against the respective criteria. If at least one of the results, for a particular parameter, exceeds the criteria, the participant will be considered as clinically notable abnormal for that parameter. A participant can be counted in both low and high categories. If multiple

abnormality occurrences exist for the same lab parameter, the worst case within a lab parameter will be used to categorize the abnormality.

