#### **2.7.4.3 Columbia Suicide Severity Rating Scale (C-SSRS)**

The Columbia-Suicide Severity Rating Scale (C-SSRS) is a questionnaire that prospectively assesses suicidal ideation and suicidal behavior. The C-SSRS must be administered at each visit, including unplanned visits. At the first study visit, the “baseline/screening” version of the C-SSRS will be administered. This version assesses suicidal ideation and suicidal behavior during the participant's lifetime and during a predefined period. At subsequent visits, the “since last visit” version will be administered. AE and SAE will be reported respectively for events of “Non-Suicidal Self-Injurious Behavior” and life-threatening events.

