##### **Summary tables**

- Summary showing numbers and percentages of participants who have an answer “yes” to a suicidal behavior or ideation category at any post-baseline visit.
- The number and percentage of participants who have an answer “yes” to a suicidal behavior or ideation category for the lifetime assessment at screening will be included.

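### The planned C-SSRS outputs cannot separate new or worsened suicidal ideation from ideation that continues or recurs, chiefly for participants with items 1-3 only

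*Protocol*

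**What the plan says.** **Entry.** Exclusion 8 (Protocol 5.2 and Protocol summary) removes people with a 'yes' on ideation item 4 or 5, with the wording "Suicidal Ideation section of the Columbia Suicide Severity Rating Scale (C-SSRS), if this ideation occurred in the past 6 months from the Screening visit". It also removes those with suicidal behavior, other than non-suicidal self-injury ("item also included in the Suicidal Behavior section), if this behavior occurred in the past 2 years"). Ideation at items 1-3 at any time, older ideation at items 4-5 and older behavior are not excluded by this criterion.

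**Administration.** The first C-SSRS covers the participant's "lifetime and during a predefined period" (Protocol 10.2.3). After that, "At subsequent visits, the “since last visit” version will be administered" (SAP 2.7.4.3). The Protocol's Table 8-2 schedules the scale at Screening, at Baseline and at later visits.

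**Outputs (SAP 2.7.4.3).** There are two summary rows. One counts participants with a 'yes' "to a suicidal behavior or ideation category at any post-baseline visit". The other counts those with a 'yes' "to a suicidal behavior or ideation category for the lifetime assessment at screening will be included". The listing gives all data, but only for participants with a 'yes' on item 4, item 5 or any behavior item.

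**The concern.** A by-arm suicidality table is read for what happened after dosing. The post-baseline row sets no new-onset or worsening condition. Someone who entered with passive ideation and reports the same on study is therefore counted exactly like someone whose ideation began on study. The lifetime row does not resolve this. It is a marginal count that does not show whether the same people appear in both rows, and its recall period differs from that of the follow-up form. The screening predefined-period answers and the Baseline-visit answers are the natural reference, and no planned table uses them.

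At stake is whether the report can show emergent ideation by treatment group. Safety and tolerability were a primary objective, and with a purely descriptive analysis the report can show only what its tables distinguish.

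**Working it through.** The documents give no C-SSRS rate, so there is no planned figure to reproduce. The check compares the texts and then gives an illustration.

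**Rules side by side (SAP)**

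| Data | Counted post-baseline | Referenced to baseline? |
|---|---|---|
| Laboratory, 2.7.3 | "newly occurring or worsening laboratory/liver enzyme abnormalities" | Yes |
| ECG, 2.7.4.1 | Newly occurring or worsening | Yes |
| Vital signs, 2.7.4.2 | Newly occurring or worsening | Yes |
| TEAEs, 2.7.1 | Onset after treatment start, or increased severity | Yes |
| Neuropathy questionnaire, 2.7.4.5 | Change from No to Yes | Yes |
| Echocardiogram, 2.7.4.1 | Any notable value | No |
| C-SSRS, 2.7.4.3 | Any 'yes' | No |

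The closest comparator is the neuropathy questionnaire, also a yes/no instrument, and it requires a change from baseline.

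**Who is affected.** Participants with item 4, item 5 or behavior are listed in full, so their earlier and later answers can be read together. Those whose only 'yes' answers are on items 1-3 are not listed, yet exclusion 8 admits them even when that ideation is current.

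**Unequal follow-up.** Protocol Table 8-5 has the C-SSRS at Weeks 33, 53 and 69 (Days 225, 365 and 477). Placebo participants may leave at Week 33, or at once if that visit is done. Branaplam participants are asked to continue. That is two further scheduled administrations on active, covering 477 − 225 = 252 more days of recall.

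**Illustration. The inputs are assumptions, not taken from the documents.** Let b be the share entering with admissible ideation, r the chance that it is reported again on study, and n the new-onset rate among the rest.

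- Rate shown in the planned row = b·r + (1 − b)·n
- Carried-over share = b·r ÷ that rate

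| b | r | n | b·r | (1 − b)·n | Rate shown | Carried over |
|---|---|---|---|---|---|---|
| 0.05 | 0.25 | 0.05 | 0.0125 | 0.0475 | 6.0% | 21% |
| 0.10 | 0.60 | 0.10 | 0.060 | 0.090 | 15.0% | 40% |
| 0.10 | 0.50 | 0.05 | 0.050 | 0.045 | 9.5% | 53% |
| 0.30 | 0.80 | 0.05 | 0.240 | 0.035 | 27.5% | 87% |
| 0.30 | 0.90 | 0.02 | 0.270 | 0.014 | 28.4% | 95% |

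The planned cohort of about 25 at 4:1 gives about 20 active and 5 placebo. In the third row, expected carried-over participants are 20 × 0.05 = 1.0 on active and 5 × 0.05 = 0.25 on placebo. The chance of at least one on active and none on placebo is (1 − 0.95^20) × 0.95^5 = 0.642 × 0.774 = 0.50, with no drug effect and equal follow-up.

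The formula treats every returning case as carried over. Some of these would have worsened and would count as emergent under the rule proposed below, so the shares are upper figures for ideation that is neither new nor worse.

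**The case against.** Several stronger readings are tempting, and the documents do not support them.

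- A reader might infer that history alone is reported as an on-study event. It is not. The follow-up form asks only about the time since the last visit, so a post-baseline 'yes' means ideation or behavior in that interval. The row is labelled as any 'yes', not as treatment-emergent. A small leak is possible: as the schedule table was extracted, the first C-SSRS after Baseline (Day -6 to -1) is at Week 2, so its recall could reach a few days before dosing.
- A reader might infer that the pre-treatment state is ignored altogether. The lifetime row is there, and the listing serves the more severe cases.
- A reader might infer that the percentage mainly reflects who entered with ideation. No rate in the documents supports that, and in some of the illustrated cases carry-over is the minority.
- With about 5 on placebo, one case moves the percentage by 1/5 = 20 points. That is equally true of a genuinely new case, and the fix does not change it.

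It is also fair to say that baseline reference is not universal in the SAP, since the echocardiogram count lacks it. Exclusion 7 lets the investigator keep out people with unstable psychiatric conditions. Life-threatening events and non-suicidal self-injury also reach the SAE and AE tables. Recurrence of older, severe ideation on study is something a safety table should show. No inferential safety comparison is planned, and suicidality is not among the important risks in Protocol Table 4-2.

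What remains is the items 1-3 group. Exclusion 8 admits these participants, the post-baseline row counts them, the listing omits them, and the stated AE/SAE routes need not capture them.

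**Conclusion.** The point holds as a gap in what the C-SSRS outputs distinguish. It is not a misstatement in the table. For participants with items 1-3 only, the planned outputs cannot tell ideation that continues or recurs from ideation that is new or worse. Longer planned follow-up on branaplam tilts the any-post-baseline count toward active even without an effect.

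The size cannot be fixed from the documents. A carried-over share of about 20% to 95% is only the span of the assumed inputs, and the 20 and 5 per group are planned numbers. Severity is minor: treatment has been stopped, the report is abbreviated and the analysis is descriptive. The change is still worth making because it is cheap and brings this scale into line with most of the SAP's other safety rules.

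**What to change.** In SAP 2.7.4.3, by treatment group:

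1. Add the number (%) with new or worsened suicidal ideation, defined as the highest post-baseline ideation item above the highest item in the pre-treatment recall period. That period is the screening predefined period plus the Baseline visit. State the length of the predefined period, which neither document gives.
2. Add, separately, the number (%) with suicidal behavior post-baseline and none in that pre-treatment period.
3. Add a shift table of worst pre-treatment by worst post-baseline category: none, ideation 1-3, ideation 4-5, behavior. Keep non-suicidal self-injury separate.
4. Keep the any-post-baseline and lifetime rows as supportive.

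The cost is one derived variable and one extra table, with no new assessment. The change removes the carry-over of continuing ideation. It does not remove the longer window for new events on active, so the new rows should be read with the follow-up time in each group.
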